9.2.1 Adverse events that do not require reporting

Events or reactions listed in the SmPC of Sodium valproate or that of the antipsychotic drug will not be reported. The period for AE reporting will be from screening until 60 days post final IMP administration.

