Adverse events will be collected for each subject. Subjects should be queried in a non-leading manner, without specific prompting (e.g., "How are you getting on with the medication?"). AEs and SAEs will be monitored throughout the study at all visits. Pretreatment events will be monitored prior to the first dose of study drug.

Clinical Laboratory Assessments

The clinical laboratory tests required by protocol are listed in Section 7.2. Blood and urine samples will be collected for clinical laboratory tests. All clinical laboratory tests will be performed locally except for the post-hoc metabolic, pharmacogenomic & drug level analysis. For detailed instructions regarding clinical laboratory procedures, sampling, and shipping guidelines refer to the study centre laboratory manual based on local clinical laboratory guidelines. Samples will be processed at a local laboratory and only blood samples for post-hoc analysis will be stored at the MRC London Institute of Medical Sciences (LMS), Hammersmith Hospital Campus, London where the CI holds a secondary position. Any value outside the normal range will be flagged for attention of the investigator. The investigator or appropriate designee will indicate whether or not the value is of clinical significance. If a clinical significant abnormality is found in the samples taken during the screening phase then their inclusion should be reviewed. If such were to happen during the treatment phase then they will be recorded as an adverse event (AE) and if needed followed until test(s) have normalized or stabilized.

Vital signs

Measurements will consist of systolic and diastolic blood pressure, respiratory rate and pulse rate. The same arm will be used for all visits to measure blood pressure. Vital signs results assessed as clinically significant by the investigator will be reported as adverse events. Vital signs will be obtained prior to clinical laboratory collections, if any, at their respective time-points.

Height, Weight, and BMI

Height will be measured in meters without shoes and will be recorded at screening. Weight will be measured in kilograms as specified in the Trial Schedule and will be done in street clothes, without shoes and coat/jacket. BMI will be calculated by site staff using the equation BMI = kg/m^2 where kg is a person's weight in kilograms and m^2 is their height in metres squared.

Pregnancy prevention and contraception

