The KHP-CTO will ensure that the CI promptly notifies all other investigators, REC and MHRA of any findings that may affect the health of subjects. A concise safety analysis and risk-benefit evaluation describing all new findings related to the safety of the IMP treatment with respect to their impact for the subjects will be considered by the PIs, CI and DMEC (if applicable).

Reporting Responsibilities

SLAM & KCL have delegated the delivery of the Sponsor's responsibility for Pharmacovigilance (as defined in Regulation 5 of the Medicines for Human Use (Clinical Trials) Regulations 2004 to the King's Health Partners Clinical Trials Office (KHP-CTO).

All SAEs, SARs and SUSARs will be reported immediately (and certainly no later than 24hrs) by the Investigator to the KHP-CTO and CI for review in accordance with the current Pharmacovigilance Policy. This includes completion of an SAE form and sent immediately to the KHP-CTO

by fax on [name]

or by email: [contact]

The original SAE Report Form will be filed in the Trial Master File, with copies filed in the patient's hospital notes, the case record form, the Investigator Site File (if applicable) and the Sponsor file.

The KHP-CTO will report SUSARs to the MHRA. The Chief Investigator will report to the relevant ethics committee. Reporting timelines are as follows:

- SUSARs which are fatal or life-threatening must be reported not later than 7 days after the sponsor is first aware of the reaction. Any additional relevant information must be reported within a further 8 days.
- SUSARs that are not fatal or life-threatening must be reported within 15 days of the sponsor first becoming aware of the reaction.

The Chief Investigator and KHP-CTO (on behalf of the *co*-sponsors), will submit annual progress report relating to this trial to the REC and will contain a summary of AEs that occur in that period.

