9.3 Treatment Stopping Rules

The trial may be prematurely discontinued by the Sponsor, Chief Investigator or Regulatory Authority based on new safety information or for other reasons given by the Data Monitoring & Ethics Committee / Trial Steering Committee regulatory authority or ethics committee concerned.

If the trial is prematurely discontinued, active participants will be informed and no further participant data will be collected. All participants will be down titrated in a similar manner discussed in Section 5.2. The Competent Authority and Research Ethics Committee will be informed within 15 days of the early termination of the trial.

10 Statistics

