The Trial Steering Committee (TSC) will be constituted in accordance with the NIHR HTA programme guidance before the start of the trial. The TSC chair will be an experienced independent member and the majority of the TSC members (75%) will be independent of the trial. At least one individual who can contribute as a patient or carer perspective will be included. In the initial stage of the trial (first six months) the TSC will review progress with respect to trial recruitment and retention and recommend changes if needed to the protocol and conduct of the trial. Thereafter it will be convened periodically at least once a year to monitor progress. The TSC will provide overall supervision of the trial and monitor trial progress and conduct and advise on scientific credibility. In the event of serious adverse events, or on the advice of the Data Monitoring and Ethics Committee, the TSC will direct action to be undertaken to ensure safety of the participants and will review trial continuation.

12 Data Monitoring Committee

A Data Monitoring and Ethics Committee (DMEC) will be constituted in accordance with the NIHR HTA programme guidance before the start of the trial. It will be the only independent body involved in the trial that will have access to the unblinded comparative data. An independent clinician in the relevant area and an expert trial statistician will be part of the committee. It will meet initially six months after the trial start and then at least once a year to monitor trial data and make recommendations to the TSC with regards to 1) recruitment of patients, 2) ethical issues in the overall conduct of the trial, 3) quality of data (including missing data), 4) incidence of adverse events and 5) any factors that may compromise the progress and satisfactory completion of the trial. The pharmacokinetic and pharmacodynamic interaction between antipsychotics and sodium valproate will be specifically monitored during the trial.

13 Patient and Carer involvement

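### Section 9.2.1 exempts every SmPC-listed event from reporting, whatever its seriousness, against the 24-hour duty in 9.2; separately, 9.3 ends data collection that 9.2.1 still requires

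*Protocol*

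**What the plan says.** Section 9.2.1 has two sentences. The first is the exemption: "Events or reactions listed in the SmPC of Sodium valproate or that of the antipsychotic drug will not be reported". The second sets a time window: "The period for AE reporting will be from screening until 60 days post final IMP administration".

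Other sections set these duties:

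- **Section 9.2, Reporting Responsibilities:** "All SAEs, SARs and SUSARs will be reported immediately (and certainly no later than 24hrs) by the Investigator to the KHP-CTO and CI". No exception is made for expected events. The same part requires an annual progress report to the ethics committee, which "will contain a summary of AEs that occur in that period".
- **Section 9.1:** "Adverse events will be collected for each subject", with monitoring at all visits. Vital-sign results that the investigator judges clinically significant are to be reported as adverse events. Clinically significant laboratory findings during treatment are to be recorded as adverse events.
- **Section 12:** the DMEC's remit includes the "incidence of adverse events".
- **Section 9.3:** if the trial is stopped early, "active participants will be informed and no further participant data will be collected", while all participants are to be down-titrated.

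**The concern.** The exemption turns on one property only, namely whether the event is listed. Seriousness, causality and the recipient of the report play no part. It covers the valproate SmPC and that of the patient's antipsychotic. Sections 4.2 and 5.7 allow antipsychotics to be switched or added, so the exempt list differs between patients and can change over time.

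The harms that matter most for oversight of an established drug are the known serious ones, and these are the events on which 9.2 and 9.2.1 give opposite instructions. Sites that follow 9.2.1 will send fewer reports than sites that follow 9.2. The sponsor's office, the annual summary and the DMEC would then work from an incomplete and uneven count.

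Section 9.3 raises a separate issue of the same kind. It permits a stop on new safety information, yet it ends data collection at the point where patients are still coming off the drug and the 60-day window is open.

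**Working it through.** No sample size, power or error rate enters this point, so the check sets the passages side by side.

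**Step 1. What reporting means in 9.2.1.** If it meant only expedited reports to the regulator, the exemption would be ordinary. The section's second sentence speaks of the period for AE reporting in general, and the section heading concerns adverse events at large. The text does not confine the exemption to expedited reports.

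**Step 2. Whether serious events fall under it.** Section 9.1 cites the SmPC in its paragraph on severe liver damage, including hepatic failure with fatalities, and again for leucopenia and agranulocytosis. Serious reactions linked to the SmPC by the protocol itself are therefore within the exemption as written.

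**Step 3. One case under each rule.** Take a serious agranulocytosis for which a relation to the trial drug cannot be ruled out.

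| Rule | Result |
|---|---|
| 9.2 definitions and Reporting Responsibilities | Consistent with the SmPC, so a SAR and not a SUSAR; to the KHP-CTO within 24 hours |
| 9.2.1 | Listed in the SmPC; not reported |
| Appendix 2 | Consistent with the SmPC, so classed as unexpected |

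The three entries cannot all be followed. If listed SARs are exempt, the duty in 9.2 to report SARs shrinks to SUSARs. Appendix 2 reverses the definition in 9.2, where an unexpected reaction is one not consistent with the SmPC. A serious suspected reaction so classed would enter the 7- or 15-day SUSAR timelines.

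**Step 4. The conflict within 9.1.** A clinically significant vital-sign change is to be reported as an adverse event. If it is also SmPC-listed, 9.2.1 says the opposite. The laboratory sentence is a weaker case, because it requires recording and 9.2.1 speaks of reporting.

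**Step 5. What does not depend on 9.2.1.**

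- The planned adverse-effect outcome is the clinician-rated UKU scale of 48 symptoms at baseline, 3, 6 and 12 months (4.1.2).
- BMI is a secondary outcome.
- Liver tests and blood counts are scheduled at 3 and 12 months or early exit (4.3, 5.3).
- Discontinuation for adverse effects is recorded (4.1.2).

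**Step 6. What does depend on reports.** Section 9.1 puts the period of maximum liver risk at 2 to 12 weeks. After screening, the first scheduled liver test is at 3 months (week 13). Earlier liver failure would be found by symptom-triggered testing and would reach oversight through AE and SAE reports. Pancreatitis is named in 9.1, but amylase is not among the tests in 7.2. Whether the SmPC lists pancreatitis is an assumption, since the SmPC is not among the documents.

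**Step 7. Section 9.3.** After early termination no further data are collected. Section 9.2.1 runs AE reporting to 60 days after the last dose. Section 9.2 follows pregnancies to term and events until recovery or stabilisation. Down-titration continues under 9.3 itself. These cannot all be followed.

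**The case against.** The strongest reply is that 9.2.1 is loose wording about non-serious adverse events. The protocol uses AE and SAE as distinct terms, and 9.2 gives a complete SAE procedure with no exception for expected events. Section 6.5 has SAE outcomes recorded for the DMEC and TSC. That reading may well be the intention. It does not cure the text: the exemption says events or reactions without qualification, and a site has no stated rule for choosing between the two sections.

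The reply does defeat three stronger readings that a reader might infer.

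- **That known harms drop out of the arm comparison and bias it towards no difference.** Section 9.2.1 says reported, not recorded, and 9.1 still collects adverse events for each subject. The UKU, BMI and laboratory measures in step 5 are unaffected.
- **That the DMEC would be blind to known harms.** Section 12 gives it unblinded comparative data and a remit to monitor trial data, and section 6.5 supplies SAE outcomes. The risk is confined to incidence counts built from reports.
- **That the loss can be sized from the platelet figure.** Section 9.1 gives a platelet decrease in 10-15% of long-term users. Applied to 181 randomised to valproate, this is 0.10 × 181 = 18.1 to 0.15 × 181 = 27.2. With about 145 per arm at one year it is 14.5 to 21.8. These are platelet falls, not adverse-event reports. Only clinically significant findings become adverse events, section 9.1 sets clinical review below 75,000/mm³, and the scheduled counts capture falls in any case. The documents do not tie this effect to the SmPC.

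On 9.3, it is fair that yellow-card reporting continues after the trial ends, and that pregnancy follow-up is already provided for. The general prohibition on further data still contradicts those provisions and the 60-day window.

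**Conclusion.** The contradiction holds. As written, 9.2.1 cannot be reconciled with the 24-hour duty in 9.2 or with the vital-signs rule in 9.1. On a literal reading, expected serious reactions could go unreported to the KHP-CTO and be absent from the annual summary and from the AE incidence put to the DMEC. Appendix 2 makes it worse by reversing the meaning of unexpected.

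The consequence is for safety oversight and not for the planned adverse-effect analysis. Its size cannot be stated, because the documents give no rate of reportable listed events and do not show how sites would resolve the conflict. The conclusion assumes only that the SmPC lists the reactions for which section 9.1 cites it.

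The conflict between 9.3 and the 60-day window is a separate defect and stands by itself.

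**What to change.** 1. **Section 9.2.1.** State that all adverse events are recorded in the CRF; that only non-serious SmPC-listed events are exempt, and only from individual onward reporting; and that every SAE and SAR stays under the 24-hour duty whatever its expectedness. Make clear that the annual AE summary and the DMEC's incidence tables draw on all recorded events.
2. **Appendix 2.** Correct the final classification so that it agrees with the definition of an unexpected adverse reaction in 9.2.
3. **Section 9.3.** Reconcile the clause on data collection with 9.2 and 9.2.1, so that AE and SAE collection to 60 days after the last dose, and pregnancy follow-up, continue after early termination.

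The cost is a protocol amendment, a note to sites and some additional adverse-event data entry. The CRF, the SAE form and the 60-day contact already exist.

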9.3 Treatment Stopping Rules

The trial may be prematurely discontinued by the Sponsor, Chief Investigator or Regulatory Authority based on new safety information or for other reasons given by the Data Monitoring & Ethics Committee / Trial Steering Committee regulatory authority or ethics committee concerned.

If the trial is prematurely discontinued, active participants will be informed and no further participant data will be collected. All participants will be down titrated in a similar manner discussed in Section 5.2. The Competent Authority and Research Ethics Committee will be informed within 15 days of the early termination of the trial.

10 Statistics

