5.2 Dosing Regimen

The two treatment arms for the trial will be sodium valproate or placebo. The IMP will be started at a dose of 500mg/day and gradually increased to a dose not exceeding 2500 mg/day over two weeks in steps of 500mg depending on body weight over a two week period (Refer to Appendix 1- Dose titration). The placebo group will receive a matching placebo titration. To ensure treatment is optimised for each patient, and to promote retention in the trial, further dose increments/decrements will be allowed in both arms at the treating clinician's discretion depending on side-effects and response and up to a maximum of 30mg/kg/day such that the dose does not exceed 2500mg/day. At the end of the 52-week treatment period, the dose of valproate will be down titrated in steps of 500mg in 3-4-day intervals by patients. The down-titration will also be done when patients exit the trial early. There are no special dietary or life-style requirements that are needed to be adhered to, but patients will be advised that alcohol intake is not recommended during treatment with valproate.

Withdrawal effects have not been reported. Nevertheless, at the end of the study or in the event of a patient wishing to discontinue valproate, the drug will be down titrated over at least two weeks to reduce the risk of a relapse.

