6.5 Withdrawal of Subjects

Participants have the right to withdraw from the study at any time for any reason. The investigator also has the right to withdraw patients from the study drug in the event of inter-current illness, AEs, SAE's, SUSAR's, protocol violations, cure, administrative reasons or other reasons. SAE's and SUSAR's will be followed up until resolution and outcomes will be recorded for the DMEC and TSC to review. It is understood by all concerned that an excessive rate of withdrawals can render the study un-interpretable; therefore, unnecessary withdrawal of patients should be avoided. In the event of hospitalization of patients unrelated to the study drug, patients will be reviewed for their continuation in the study and, if needed, will be recommended for a drug holiday as described in the next paragraph. Should a patient decide to withdraw from the study, the reason for withdrawal will be recorded in the exit interview if they provide us with one. Should a patient discontinue from study drug only, efforts will be made to continue to obtain follow-up data, with the permission of the patient.

Poor compliance (no minimum threshold) will not merit withdrawal but will be recorded and follow-up data will be continued to be obtained. Study drug holiday is permissible in case of an emergency, or for elective surgery or medical procedures. The process for the drug holiday is that when subjects will undergo a down titration till IMP is completely stopped as described in Section 4.3 and will then be up titrated when they re-join the

study. In such cases their assessments will be delayed depending on the study drug holiday period.

6.6 Expected Duration of Trial.

The total duration of the trial is expected to be 5 years. The end of the trial will be defined as last patient to complete visit 7 (V7), including the 60-day follow-up period to assess AE/SAEs after the last day of medication. Each individual subject will remain on the active trial for 12 months, +/- two weeks for the discontinuation of the treatment at the end. Long-term annual follow-up using clinical and electronic records will be conducted up to the point where the last patient completes Visit 7 for the entire trial.

7 Trial Procedures

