An optional urine pregnancy test will be available in case the patient does not want to give blood samples or if there is a delay from when the serum pregnancy test was done at the start of the trial. Pregnancy risks will be reviewed at each time-point and a urine pregnancy test will be conducted based on risk assessment if needed. A valid annual risk acknowledgement plan must be in notes for medication to be dispensed. Pregnancy if it were to occur will lead to rapid down titration and stoppage of medication and though not an SAE it will also be reported via the SAE reporting system (pregnancy is not regarded as an AE unless there is suspicion that the medication may have interfered with the effectiveness of a contraceptive medication). Pregnancy will be monitored till term and if a live birth occurs, the infant may be followed over a period of 5 years and monitored for the detection of birth defects and other functional or developmental deficits. Reporting beyond the study period will be done using the yellow card scheme.

Columbia-Suicide Severity Rating Scale (C-SSRS)

The Columbia-Suicide Severity Rating Scale (C-SSRS), an evidence-supported tool, is a simple series of questions that rates suicide risk and is commonly used to identify suicide risk [48]. The C-SSRS will be offered at baseline, 3-month, 6-month and 12-month time point to assess suicide risk. The scale takes approximately 5 minutes to administer it. If the subject answers "yes" to "Suicide Ideation" Items 4 (active suicide ideation) with some intent to act, without specific plan) or Item 5 (active suicidal ideation with specific plan and intent) on the C-SSR then the study medication will be discontinued and will be guided to seek appropriate therapy. At screening visit, "Baseline/Screening" version of C-SSRS will be used which includes assessment for lifetime and previous 1 month. For all visits from Visit 2 onwards, the "since last visit" version of the C-SSRS will be used.

UKU Side effect rating scale

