Participants will be followed up until clinical recovery and laboratory results have returned to normal baseline values, or until the event has stabilized. If the investigator believes that an SAE is not related to the study drug, but potentially related to the conditions of the study (such as withdrawal), the relationship will be specified in the narrative section of SAE report form. Pregnancy will be monitored till term and if a live birth occurs, we may request the infant to be followed up to a period of 5 years and monitored for the detection of birth defects and other functional or developmental deficits. After the end of the trial, any subsequent events that may be attributed to treatment will be reported to the MHRA using the yellow card system.

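### Section 9.3 ends all participant data collection if the trial is stopped early, even for safety, which conflicts with the protocol's own safety follow-up of about 60 to 80 days after such a stop

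*Protocol*

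**What the plan says.** Section 9.3 lets the sponsor, chief investigator or regulator stop the trial early "based on new safety information or for other reasons given by the Data Monitoring & Ethics Committee" or by the other bodies it names. On such a stop, "active participants will be informed and no further participant data will be collected". The next sentence reads: "All participants will be down titrated in a similar manner discussed in Section 5.2". Section 5.2 says that at the end of the study, or when a patient wishes to discontinue, "the drug will be down titrated over at least two weeks to reduce the risk of a relapse".

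Elsewhere the protocol sets these safety follow-up rules:

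- **9.2.1:** "The period for AE reporting will be from screening until 60 days post final IMP administration".
- **4.3, Table 1 footnote and 7.1 (Visit 7):** one contact, 60 days after the last intake of study drug, to record AEs and SAEs. Section 7.1 applies the Visit 6 and Visit 7 steps to early exit, if the patient consents.
- **6.5:** "SAE's and SUSAR's will be followed up until resolution and outcomes will be recorded for the DMEC and TSC to review".
- **9.2 (Reporting Responsibilities):** "Participants will be followed up until clinical recovery and laboratory results have returned to normal baseline values, or until the event has stabilized".
- **9.1 (Pregnancy prevention and contraception):** "Pregnancy will be monitored till term and if a live birth occurs, the infant may be followed over a period of 5 years". Section 9.2 also has each pregnancy followed to its outcome.
- **4.3 and 5.3:** liver function and full blood count are tested when a participant exits early.

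None of these rules makes an exception for early termination, and 9.3 refers to none of them.

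**The concern.** A stop for safety is the situation in which complete follow-up matters most, and it is the only situation in which 9.3 switches data collection off. Participants would still be taking tablets during the taper and would then be inside the period that the protocol treats as reportable.

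Three things are at stake.

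- **The comparison between arms.** AEs would be truncated at the decision date, although the committees would need the fullest comparison of valproate with placebo.
- **Events already open.** Section 9.2 expects further information on a fatal or life-threatening SUSAR within 8 days of the first report. A site that has stopped collecting cannot readily supply it. Pregnancies matter particularly because 5.3 acknowledges the teratogenic risk.
- **Exit blood tests.** Section 9.1 puts the period of greatest hepatic risk at 2 to 12 weeks. The screening liver test is at the clinician's discretion, and the first scheduled on-treatment test is at 3 months. Section 9.1 adds a test triggered by symptoms. A participant without symptoms whose trial ends before the 3-month visit would therefore have no scheduled on-treatment liver test unless the exit test is done.

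**Working it through.** The plan gives no figure to reproduce here. The check sets the passages side by side and then works out how long the affected window lasts.

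**Step 1: order of events under 9.3.** The trial stops, collection ends, and participants taper. A participant on study drug at the stop is therefore still taking it after collection has ended.

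**Step 2: set the rules side by side.**

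| Item | Rule elsewhere in the protocol | 9.3 read literally |
|---|---|---|
| AEs | To 60 days after last dose (9.2.1) | None after the stop |
| AE/SAE contact | 60 days after last intake (4.3, Table 1, 7.1) | Not made |
| SAEs and SUSARs | To resolution (6.5) | Not followed |
| Other events | To recovery or stabilisation (9.2) | Not followed |
| Pregnancy | To term or known outcome (9.1, 9.2) | Not followed |
| Liver function, blood count | At early exit (4.3, 5.3) | Not done as trial data |

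Both columns cannot be followed at once.

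**Step 3: length of the window.** The inputs are 500 mg tablets, 1 to 5 tablets a day (maximum 2500 mg/day), reductions of 500 mg at 3- to 4-day intervals (4.3, 5.2), and 60 days after the last dose (9.2.1). Let *n* be the number of tablets a day at the stop.

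- Shortest taper, with the first reduction on the day of the stop and 3-day intervals: 3 × (*n* − 1) days.
- Longest taper, with one full 4-day interval per tablet: 4 × *n* days.
- End of the AE window after the stop: taper + 60 days.

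| Daily dose at stop | Taper (days) | Window ends (days after stop) |
|---|---|---|
| 500 mg | 0 to 4 | 60 to 64 |
| 1000 mg | 3 to 8 | 63 to 68 |
| 1500 mg | 6 to 12 | 66 to 72 |
| 2000 mg | 9 to 16 | 69 to 76 |
| 2500 mg | 12 to 20 | 72 to 80 |

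The window thus runs about 60 to 80 days past the stop. Under the 5.2 minimum of two weeks it is at least 14 + 60 = 74 days. Section 4.3 instead describes a taper of up to two weeks. The two descriptions differ and need reconciling, but the conflict with 9.3 exists under either.

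**Step 4: look for text that resolves the conflict.** Sections 9.1 and 9.2 provide for Yellow Card reports after the study period. The provision in 9.2 covers later events that may be attributed to treatment. That is spontaneous reporting of selected events. It does not replace asking every participant in both arms at 60 days, or following an open event to its outcome. No passage says that safety follow-up continues after a stop under 9.3.

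**The case against.** The strongest reply is that 9.3 revokes nothing. The rules in 6.5, 9.1, 9.2 and 9.2.1 are unconditional, so they can be read as still in force, with the sentence in 9.3 ending only scheduled trial visits. Section 9.3 also sends participants to the taper in 5.2, which applies to early exit, and early exit carries blood tests and the 60-day contact. The pregnancy record is held by the trials office that has been delegated pharmacovigilance. The steering committee can direct action for participants' safety, and Yellow Card reporting remains.

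Much of this stands, and it rules out stronger readings:

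- A reader might infer that 9.3 cancels the safety follow-up. The documents do not say so. They contain rules that conflict.
- A reader might infer that every open SAE and every pregnancy would lose its outcome. The trials office's pregnancy record and the Yellow Card route mean this is not shown.
- A reader might want a count of participants affected. Even accrual of 362 over about 3 years would put 362/3 × 54/52 ≈ 125 on study drug at a mid-recruitment stop if nobody had left treatment early. The protocol gives no accrual pattern, a stop at another time could affect far fewer, and the point does not depend on this number.

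The reply does not remove the conflict. The words in 9.3 cover participant data without qualification, and nothing says that a trial-wide stop counts as early exit. Site staff would have to guess which rule governs, at the moment with least time to ask.

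**Conclusion.** The point holds as an internal conflict in the protocol. Followed literally, 9.3 ends safety data collection while participants are on study drug or have just stopped it, including after a stop for safety. The protocol's other sections require collection for about 60 to 80 days past the stop for a participant on drug, and longer for unresolved events and pregnancies.

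The 60 to 80 days assumes that tapering starts at the stop decision and follows the stated steps. A more rapid reduction, which the protocol allows for clinical reasons, would shorten the taper part, and someone already off drug has less than 60 days left. The conflict itself needs no assumption beyond the plain wording.

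The clause matters only if the trial is stopped early. It has no bearing on randomisation, power or the primary analysis of a completed trial. It still needs correcting in advance, because a safety-driven stop leaves little time to amend the protocol.

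**What to change.** Amend 9.3 to say which data collection stops and which continues. For example:

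> If the trial is stopped early, collection of efficacy and other non-safety data ends. The safety follow-up set out elsewhere in this protocol continues for participants who agree to it: the safety assessments at early exit, collection of AEs and SAEs to 60 days after the last dose, and follow-up of open SAEs, SUSARs and pregnancies under sections 6.5, 9.1 and 9.2.

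The sponsor should mark which of the existing early-exit assessments in Table 1 count as safety assessments. No new assessment is needed, and neither the end-of-trial definition nor any dose, taper or other clinical rule has to change for this fix.

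The cost is one short protocol amendment. Beyond that there is a cost only if the trial stops early, and then for exit visits and calls already in the schedule and for event and pregnancy follow-up that the protocol already requires.
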